18.3 Handling of Missing, Unused, and Spurious Data

All statistical analysis will generally be based on observed values, missing values will not be imputed. In case of >5% of missing values for an immunogenicity comparison involving a statistical test, multiple imputation methods will be applied in order to evaluate the possible impact of missing values on these results.

18.4 Methods of Analysis

A statistical analysis plan will be prepared before database closure/snapshot.

18.4.1 Primary Endpoint

The primary immunogenicity analysis will be a comparison of the GMTs in the per-protocol (PP) analysis set between the VLA1553 Lots 1, 2 and 3 at Day 29 (i.e. 28 days post-vaccination) by ANOVA (factor Lot, covariate study site). The ANOVA model will be applied to the log10-transformed μ PRNT values of the three Lots and the 95% CIs for the pair-wise ratios of the GMTs will be obtained by taking the anti-log of the resulting 95% CIs for the least square means differences. If these three pairwise 95% CIs for GMT ratios are all between [REDACTED], equivalence between the three commercial batches will be postulated.

The analysis will be performed on the PP population who were baseline negative for CHIKV antibodies and will be repeated on the full analysis set.

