10.4.1 Selection of Study Population

A total of approximately 402 healthy subjects of either gender, 18 to 45 years of age, who meet all inclusion criteria and none of the exclusion criteria and provide a written informed consent, will be invited to participate in the study. Subjects who have a history of CHIKV infection, including a suspected CHIKV infection or subjects who are taking medication or other treatment for unresolved symptoms attributed to a previous CHIKV infection will be excluded. Subjects will be screened for their CHIKV sero-status at study entry, subjects tested positive for CHIK will be excluded from the primary endpoint analysis.

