12.3 Study Endpoints

12.3.1 Primary Endpoint

Immunogenicity

The primary endpoint is the Geometric mean titer (GMT) of CHIKV-specific neutralizing antibodies as determined by μ PRNT assay on Day 29 post-vaccination in subjects who tested negative for CHIKV antibodies at baseline.

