18.2 Datasets and Analysis Cohorts

The full analysis set contains all subjects who were randomized and received at least one vaccination. Subjects will be analyzed as randomized.

The safety analysis set contains all subjects who entered into the study and received at least one vaccination. Subjects will be analyzed as treated.

The per protocol (PP) analysis set contains all subjects who were baseline negative for CHIKV antibodies and have received the vaccination and have evaluable immunogenicity data at baseline and the time point for the primary endpoint without a major protocol violation. Examples that may lead to exclusion from the PP population are provided here, further criteria may be defined in the Statistical Analysis Plan (SAP):

- Subject has a known or suspected defect of the immune system that can be expected to influence the immune response to the vaccine, such as subjects with congenital or acquired immunodeficiency, including infection with HIV, status post organ transplantation or immuno-suppressive therapy within 4 weeks prior to Visit 1. Immuno-suppressive therapy is defined as administration of chronic (longer than 14 days) prednisone or equivalent ≥ 0.05 mg/kg/day within 4 weeks prior to study entry, radiation therapy or immunosuppressive cytotoxic drugs/ monoclonal antibodies in the previous 3 years; topical and inhaled steroids are allowed;

- Subject is positive for human immunodeficiency virus (HIV), hepatitis B surface antigen (HBsAg) or hepatitis C virus (HCV);
- Subject has received the wrong (not according to randomization) or no IMP.

These criteria for protocol violations are identified at the time of planning the study. However, during the course of the trial unforeseen events may occur or new scientific knowledge may become available, therefore final decisions on whether a protocol violation could impact on the immune response and thus lead to exclusion from the PP population will be made by the sponsor on a case by case basis in a blinded manner (prior to study unblinding). Sample testing issues may also lead to exclusion from the PP analysis for particular time points.

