9.2 Primary Endpoint

The primary immunogenicity endpoint is the geometric mean titer (GMT) of CHIKV-specific neutralizing antibodies as determined by μ PRNT assay on Day 29 post-vaccination in subjects who tested negative for CHIKV antibodies (as determined by ELISA) at baseline.

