9.4.2 Full Analysis Set

The full analysis set (FAS) contains all subjects who were randomized, received the vaccination and have evaluable immunogenicity data at the time point for the primary endpoint. Subjects will be analyzed as randomized.

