13.4.2 Primary Immunogenicity Analysis

The primary immunogenicity analysis will be a comparison of the GMTs in the PP analysis set between the VLA1553 Lots 1, 2 and 3 at Day 29 (i.e. 28 days postvaccination) by ANOVA, using the factor Lot as a fixed effect and study center as a covariate. The ANOVA model will be applied to the log-transformed (natural log base e) μ PRNT values of the three Lots and the 95% CIs for the pair-wise ratios of the GMTs will be obtained by taking the anti-log of the resulting 95% CIs for the least square means differences. If these three pairwise 95% CIs for GMT ratios are all between [REDACTED] equivalence between the three commercial batches will be postulated.

The analysis will be performed on the PP analysis set and will be repeated on the Full analysis set.

For the PP analysis set there will be also produced the following graphical outputs:

- a line plot of the GMT at each study timepoint and treatment arm;
- a reverse cumulative distribution plot of the proportion of subjects by treatment arm.

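### The full-analysis-set repeat of the GMT and GMFI lot comparisons carries no baseline serostatus condition, although the primary endpoint is defined in seronegative subjects

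*Protocol*

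**What the plan says.** - **Endpoint.** Protocol 12.3.1 defines the Day 29 GMT "in subjects who tested negative for CHIKV antibodies at baseline". SAP 9.2 names the test: "in subjects who tested negative for CHIKV antibodies (as determined by ELISA) at baseline".
- **Seropositive subjects.** A positive screening ELISA does not bar enrolment. Protocol 10.4.1 says that "subjects tested positive for CHIK will be excluded from the primary endpoint analysis", and the sample size sections (Protocol 18.1, SAP 8.1) allow for 2% of them.
- **PP set.** Protocol 18.2 and SAP 9.4.3 limit it to baseline-negative subjects. SAP 9.4.3 makes it the primary set for immunogenicity.
- **FAS.** Protocol 18.2: "The full analysis set contains all subjects who were randomized and received at least one vaccination". SAP 9.4.2 adds a Day 29 data requirement: it "contains all subjects who were randomized, received the vaccination and have evaluable immunogenicity data at the time point for the primary endpoint". Neither mentions serostatus.
- **Repeat.** In Protocol 18.4.1 the primary analysis is for PP subjects who were "baseline negative for CHIKV antibodies and will be repeated on the full analysis set". SAP 13.4.2: "The analysis will be performed on the PP analysis set and will be repeated on the Full analysis set". The model contains lot and study center only. SAP 13.4.3 repeats the secondary immunogenicity analyses on the FAS as well, and SAP 13.4.3.1 treats GMFI like GMT.

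**The concern.** Protocol 10.4.1 keeps seropositive subjects out of the primary endpoint analysis, but the documents carry that out only through the PP set. Once the analysis moves to the FAS, nothing visible keeps them out or adjusts for them. The repeat then estimates a lot ratio in a wider population than the endpoint names.

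In an equivalence trial, a reader uses the FAS result to see whether per-protocol exclusions shaped the conclusion. That comparison is cleanest when the two sets differ only in those exclusions. Here they also differ in serostatus, which is part of the endpoint definition. A seropositive subject's Day 29 titer, and still more the fold increase, may say more about past infection than about the lot received.

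The SAP does condition on serostatus elsewhere. Seroprotection is restricted to µPRNT-negative subjects (SAP 11.6.4, 13.4.3.2), seroconversion has separate definitions by baseline status (SAP 11.6.3), and the AE summary table is split by ELISA status (SAP 13.5.1). The FAS comparisons of GMT and GMFI have no such condition.

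**Working it through.** **The plan's own figure.** Inputs from Protocol 18.1 are 134 per lot, SD 0.32 log10, 10% drop-out, 5% major deviations, 2% seropositive, two-sided 5%, and about 90% overall power. Evaluable PP per lot = 134 × 0.90 × 0.95 × 0.98 = 112. The margin is redacted, so the power cannot be reproduced outright. Solved backwards with identical lots, 90% needs a GMT-ratio margin of about 1.49. A margin of 1.5 gives about 92%. I use 1.5 below as an assumption.

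**Set sizes per lot.**
- FAS with Day 29 data: 134 × 0.90 = 120.6, about 121.
- Seronegative FAS: 120.6 × 0.98 = 118.
- Seropositives: 0.02 × 402 = 8.0 randomized, or 0.02 × 361.8 = 7.2 with Day 29 data; about 2.4 per lot.

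**Precision, Day 29 GMT.** The documents give no titer distribution for seropositives, so I assume a shift d (log10, either direction) and the same SD:

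SD = √(0.32² + 0.02 × 0.98 × d²); CI half-width = 1.96 × SD × √(2/n).

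Reference half-widths: PP (n = 112) 0.0838; seronegative FAS (n = 118) 0.0817.

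| d | SD | Half-width, FAS n = 121 | vs PP | vs seronegative FAS |
|---|---|---|---|---|
| 0 | 0.320 | 0.0806 | 0.96 | 0.99 |
| 0.3 | 0.323 | 0.0813 | 0.97 | 1.00 |
| 0.5 | 0.328 | 0.0825 | 0.98 | 1.01 |
| 0.7 | 0.335 | 0.0843 | 1.01 | 1.03 |
| 1.0 | 0.349 | 0.0880 | 1.05 | 1.08 |
| 1.5 | 0.383 | 0.0964 | 1.15 | 1.18 |

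Break-even against PP: SD = 0.32 × √(121/112) = 0.3326, so d = √((0.3326² − 0.32²)/0.0196) = 0.65 log10, a 4.5-fold difference. Against the seronegative FAS the same formula with 118 in place of 112 gives 0.36 log10, but the loss stays at about 3% or less up to d = 0.7.

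**Chance that all three pairwise 95% CIs lie within an assumed margin of 1.5** (simulation, identical lots, pooled variance, repeatable to about one point):
- PP, n = 112: 92%.
- Seronegative FAS, n = 118: 94%.
- Unrestricted FAS, n = 121: 93% at d = 0.5, 87% at d = 1.0, 76% at d = 1.5.

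**Chance imbalance.** Three more seropositives in one lot than in another, at d = 0.5, move the ratio by 10^(3 × 0.5/121) = 1.03.

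**GMFI.** Protocol 10.3.2 reports that at least 96.3% of naive Phase 1 subjects in every dose group reached a 16-fold rise by Day 28 (log10 16 = 1.2), and that re-vaccination gave no anamnestic response. If seropositives here behave like the re-vaccinated subjects, their log fold increase sits about 1.2 or more below the rest. With d = 1.2, and assuming SD 0.32 also for fold increase, SD = √(0.1024 + 0.0196 × 1.44) = 0.361. The half-width is then (0.361/0.32) × √(118/121) = 1.11 to 1.12 times that of the seronegative FAS. Two caveats apply: the Phase 1 subjects were primed by vaccine rather than infection, and Phase 1 used a different neutralization assay (Protocol 16.1).

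**The case against.** The strongest reply is that no decision depends on the FAS repeat. Equivalence is postulated from PP, which already excludes ELISA-positive subjects, so the endpoint definition is respected where the conclusion is drawn. No success criterion attaches to the FAS, and an FAS broader than PP is normal. All of this stands, and it is why the point is minor.

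A reader might infer that the FAS repeat must be noisier than the primary analysis, or is likely to fail. The documents do not support that. The FAS has about 9 more subjects per lot than PP, so for the Day 29 GMT its CI is the narrower one until the assumed shift passes about 0.65 log10. The 87% and 76% figures need 10-fold and 32-fold shifts for which the documents give no basis.

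A reader might also infer that a PP/FAS disagreement could not be explained. It could be: ELISA status is recorded for every subject (Protocol 17.7.2), and SAP 13.1 lists the reasons for exclusion from each analysis set. The mixing of two differences is an avoidable inconvenience that can be untangled afterwards.

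Finally, SAP Table 9-1, 9.4.4 and 13.4.4 are redacted and may hold further serostatus-based analyses. SAP 11.6.3 mentions a set called sPP1 next to PP, for µPRNT-negative subjects. It appears to be a per-protocol subset, which would leave the FAS as it is. The finding is therefore limited to the readable text: the FAS definitions and the sentences that order the repeat.

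**Conclusion.** The mismatch holds on the readable text. The endpoint is defined in ELISA-negative subjects, while the FAS repeats of the GMT and GMFI comparisons have neither a serostatus condition nor a serostatus term. About 7 to 8 seropositive subjects enter if the planned 2% is right, and PP and FAS then differ in serostatus as well as in deviation exclusions.

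The consequence is small. The PP-based conclusion, the sample size and the error rate are untouched, and randomization balances seropositives across lots in expectation. For the Day 29 GMT, an assumed 0.5 log10 shift widens the CI by about 1% relative to a seronegative FAS and lowers the chance of meeting an assumed 1.5 margin from 94% to 93%. The loss becomes noticeable only at much larger shifts. For GMFI a shift above 1 log10 is plausible from the sponsor's own Phase 1 summary, so the effect is likely larger there, with a CI about 12% wider under the stated assumptions. The shift, the SD in seropositives and the margin are all assumptions.

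**What to change.** In SAP 13.4.2 and 13.4.3.1, state that the FAS repeat of the GMT and GMFI lot comparisons is done in FAS subjects who were ELISA-negative at baseline. Keep the all-FAS version as descriptive only, or add baseline serostatus as a factor in it.

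This takes one sentence in each place and a flag already needed for the PP set and the AE split. The downside is about 8 fewer subjects in a supportive analysis (about 118 instead of 121 per lot), which costs at most about 1% in CI width if seropositives turn out no different from the rest.

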18.4.2 Secondary Endpoints

18.4.2.1 Secondary Safety Endpoints

Safety tabulations will generally be provided separately for solicited AEs and unsolicited AEs, and for both types of AEs combined. 95% confidence intervals according to Altman will generally be provided for all AE rates and differences between the three Lots will be

assessed for significance using Fisher's exact test. Further details in addition to the outline below will be provided in the SAP.

The number and percentage of subjects with any AE, any solicited AE, unsolicited AE, any related unsolicited AE, any related severe AE, any SAEs, any related SAEs, any AESI, any related AESI, any medically attended AE, any AE leading to withdrawal from study, and any AE occurring at a frequency of at least 10% and at least 1% in at least one treatment group, up to Day 29, and up to Month 6, will be presented for each Lot overall and by system organ class/preferred term. Differences between the Lots will be assessed for significance using Fisher's exact test, a significant overall test will be amended by pair-wise tests.

Changes in laboratory values from study entry will be analyzed descriptively and will be part of the unsolicited AE evaluation only in case of clinically relevant deviations. The rates of subjects with laboratory assessments outside the normal range, and with abnormal laboratory parameters falling into the grade 0 vs. 1 through 3 will be calculated by visit and overall. The rate of subjects with urinalysis results according to the test manufacturer's results categories will be calculated.

All subjects entered into the study, who receive the single vaccination, will be included in the safety analysis.

18.4.2.2 Secondary Immunogenicity Endpoints

Secondary immunogenicity analysis will include the comparison of the GMTs between the three Lots at Day 8, Day 85 and Month 6 post-vaccination by ANOVA (factor Lot and covariate study site), two-sided 95% confidence intervals will be calculated for the GMT; GMFIs will be analyzed as outlined for GMTs. In addition, the seroprotection and seroconversion rates for various study days, and when applying other threshold titers for defining seroconversion or seroprotection thresholds will be compared between the treatment groups by Fisher's exact test and 95% confidence intervals will be calculated.

Analysis will be performed on the PP analysis set. It will be specified in the SAP which secondary immunogenicity analysis will be repeated for the full analysis set.

18.5 Planned Data Analysis of the Study

The following data analyses will be performed:

- Part A includes immunogenicity and safety data after all subjects have completed Visit 3 (Day 29);
- Part B includes immunogenicity and safety data after all subjects have completed Visit 5 (Month 6).

Individual study parts will be analyzed sequentially.

The Part A analysis will be performed once the last subject has completed the study Visit 3 (Day 29). Part B analysis will be performed once the last subject has completed the study Visit 5, i.e. Month 6, respectively. Part A will be unblinded but blind will be maintained for study sites.

19. ETHICS AND REGULATORY ASPECTS

19.1 Compliance Statement

This study will be conducted in accordance with this protocol, current ICH/GCP guidelines, Declaration of Helsinki, and with the applicable national and local regulatory requirements.

19.2 Institutional Review Board (IRB) and Regulatory Authorities

Before enrollment of healthy volunteers into this study, the protocol, informed consent form, any promotional material/Advertisements, and any other requested information will be reviewed and approved/given favorable opinion by the IRB and applicable regulatory authorities in accordance with local requirements. The study will commence only upon the Sponsor's receipt of approval/favorable opinion from the IRB.

If the protocol and/or any other information given to the subject is/are amended, the revised document(s) will be reviewed and approved/given favorable opinion by the IRB and applicable regulatory authorities in accordance with local requirements, where applicable. The protocol amendment will only be implemented upon the Sponsor's receipt of approval. Amendments that are intended to eliminate an apparent immediate hazard to subjects may be implemented prior to receiving IRB and authority approval. However, in this case, approval must be obtained as soon as possible after implementation.

19.3 Subject Information and Informed Consent

It is the Investigator's responsibility to obtain freely given written informed consent from the subject before the subject is exposed to any study-related procedures, including screening tests for eligibility.

The informed consent form will include a comprehensive explanation of the proposed treatment without any exculpatory statements, in accordance with the elements required by ICH GCP and applicable regulatory requirements. Volunteers will be allowed sufficient time to consider participation in the study after having the nature and risks of the study explained to them. By signing the informed consent form, volunteers agree that all evaluations required by the study will be completed, unless they withdraw voluntarily or are terminated from the study for any reason.

The Investigator will explain that the subjects are completely free to refuse to enter the study or to withdraw from it at any time, without any prejudice and need for justification.

The subjects will be informed that representatives of the Sponsor and health authority inspector may review their source records, and that these persons are bound by confidentiality obligations.

The subject will be given a copy or a second original of the ICF. An original of the signed and dated ICF must be retained in the site's records, and is subject to inspection by representatives of the Sponsor or representatives from regulatory agencies.

The Sponsor will provide to the Investigator in written form any new information that significantly bears on the subjects' risks associated with study vaccine exposure. The informed consent form will be updated, if necessary. This new information and/or revised informed consent form, that has been approved by the applicable IRB and regulatory authorities, where applicable, will be provided by the Investigator to the subjects who consented to participate in the study.

20. QUALITY CONTROL AND QUALITY ASSURANCE

20.1 Source Data and Records

Source data are defined as all information related to clinical findings, observations or other activities in the study, captured in original records or certified copies of original records. The Investigator will permit study-related monitoring, audits, IRB review and regulatory inspections, by providing direct access to source data/records. Source records should be preserved for the maximum period of time required by local regulations.

Source data entries must be made in accordance with local requirements. Signed and dated copies of the laboratory result reports have to be kept within the subject's source data file.

eCRFs will not be used as source data for any other variable.

20.2 Investigator's Responsibility

The Investigator will comply with the protocol (which has been approved/given favorable opinion by the IRB), ICH GCP, and applicable regulatory requirements. The Investigator is ultimately responsible for the conduct of all aspects of the study at the study site and verifies by signature the integrity of all data transmitted to the Sponsor. The term "Investigator" as used in this protocol, and in study documents refers to the Investigator or authorized study personnel whom the Investigator has designated to perform certain duties. Sub-investigators or other authorized study personnel are eligible to sign for the Investigator, except where the Investigator's signature is specifically required.

20.3 Training

The study monitor will ensure that the Investigator and study site personnel understand all requirements of the protocol, the investigational status of the vaccine, and his/her

regulatory responsibilities as an Investigator. Training may be provided at an Investigator's meeting, at the study site, and/or by instruction manuals. In addition, the study monitor will be available for consultation with the Investigator and will serve as the liaison between the study site and the Sponsor.

20.4 Monitoring

A designated monitor will check electronic system data and source data at regular intervals throughout the study to verify completeness, accuracy and consistency of the data, protocol adherence, and adherence to GCP guidelines. The monitor will work and perform Source Data Verification according to the Clinical Management Plan. The Investigator will cooperate with the monitor to ensure that any discrepancies identified are resolved.

20.5 Audit and Inspection

Upon request, the Investigator will make all study-related source data and records available to a qualified quality assurance auditor mandated by the Sponsor or to regulatory inspectors. The main purposes of an audit or inspection are to confirm that the rights and welfare of the subjects have been adequately protected, and that all data relevant for the assessment of safety and efficiency of the investigational product have appropriately been reported to the Sponsor.

